7.2. Handling of Dropouts or Missing Data

Missing data may have an impact upon the interpretation of the trial data. Values for missing data will not be imputed, however a methodology is defined for missing dates. All available data for subjects who do not complete the study will be included in the data listings. An analysis of the last recorded observation will be conducted to facilitate a comparison predicated on the ITT population.

Safety Data

Missing or incomplete data will not be imputed. For patients who withdraw from the study prematurely, the last recorded observation will serve as final observation.

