Ho: μ (Change in NPRS score at 4 months / PEMF group) = μ (Change in NPRS score at 4 months / sham group)

Ha: μ (Change in NPRS score at 4 months / PEMF group) $\neq \mu$ (Change in NPRS score at 4 months / sham group)

To compare the absolute change in pain from baseline to 4-months, the intra-patient change will be calculated and serve as the dependent variable in the analysis. The baseline pain score will be introduced in the model as a covariate. Clinical site will be added to the model to assess poolability of the data across sites. Interaction between clinical site and treatment will be evaluated using a type 1 error rate of 10%.

Mixed Models with Repeated Measures (MMRM) comparing results across all time-points will also be performed, adjusted for the baseline value, week, treatment by week interaction and the effect of the patient.

Sub-group analysis will be pre-specified in the SAP and will be performed on subjects with pain scores ≥ 5 as well as subjects with A1C above and below 8.5.

Missing or Incomplete Data

If a patient reports at least 3 days with non-missing pain intensity scores within a particular week, the weekly mean pain intensity score will be derived using the non-missing scores only. This is identical to imputing the missing scores as the mean of the non-missing scores. If the patient reports less than 3 days with non-missing pain intensity scores within a particular week, the weekly mean pain intensity score will be treated as missing data.

Missing weekly mean pain intensity scores will be imputed using multiple missing data and pattern mixture methodology. Sensitivity analyses will be conducted exploring different patterns for missing data. An MMRM will be performed using only observed data without multiple imputation

and an analysis using the change from baseline to the last non-missing weekly mean pain intensity score will also be provided.

The pattern mixture model methodology will be implemented using SAS procedures MI and MIANALYZE. Specifically, the following steps will be followed:

• Intermittent missing data will first be imputed using the Markov Chain Monte Carlo (MCMC) method implemented with the SAS MI procedure, which is appropriate for non-monotonic missing data.

Data for patients who discontinues early will be multiply imputed as follows:

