- If the patient discontinues due to an AE lack of response, then missing data will be assumed to follow a distribution similar to the baseline values observed in the patient's randomized treatment.
- If the patient discontinues due to reasons other than AE or treatment response, at each time point, missing data will be assumed to follow a distribution similar to scores for patients that are still in the study and randomized to the same treatment group.

Results of the 120-day results, and the MMRM using the multiply imputed data, will be summarized using the SAS MIANALYZE procedure.

A hierarchical approach will be undertaken for the pre-specified secondary outcomes. Testing will occur in the listed sequence following testing of the primary endpoint.

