The Level 3 displays will report the paired results for the change from the baseline through Month 4. For example, if 18 subjects complete the baseline evaluation and 16 subjects complete the Month 4 visit, the difference (Month 4 minus Baseline) will contain 16 subjects.

Supportive individual subject data listings will be sorted and presented by subject number and visit date, if applicable. Listings will also include the number of days relative to the initial study treatment (active or sham).

Specific algorithms are discussed for imputing missing or partially missing dates, if deemed appropriate, under specific data topics. Imputed or derived data will be flagged in the individual subject data listings. Imputed data will not be incorporated into any raw or primary datasets. The imputed data will be retained in the derived / analysis datasets.

The total duration for a subject *on-study* will be calculated as the difference between the date of initial study treatment (active or sham) and the last day of observation plus 1 day. All calculations for defining the duration on-study will follow the algorithm DURATION = [STUDY COMPLETION OR WITHDRAW DATE – INITIAL TREATMENT DATE + 1].

This section details general conventions to be used for the statistical analyses. The following conventions will be applied to all data presentations and analyses.

- Summary statistics will consist of the count and percentage in each level for categorical variables, and the sample size (n) mean, median, standard deviation (SD), minimum, and maximum values for continuous variables.
- All mean and median values will be formatted to one more decimal place than the measured value. Standard deviation values will be formatted to two more decimal places

than the measured value. Minimum and maximum values will be presented with the same number of decimal places as the measured value.

- The number and percentage of responses will be presented in the form XX (XX.X%).
- All probability values will be rounded to four decimal places. All p-values that round to 0.0000 will be presented as '<0.0001' and p-values that round to 1.0000 will be presented as '>0.9999'. P-values <0.05 will be considered to be statistically significant.
- All summary tables will include the analysis population sample size (i.e., number of subjects).

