11. EFFICACY EVALUATIONS

The primary endpoint for the study is the change from baseline in the NPRS score at 4 months. The primary hypothesis to be tested is presented below:

Ho: μ (Change in NPRS score at 4 months / PEMF group) = μ (Change in NPRS score at 4 months / sham group)

Ha: μ (Change in NPRS score at 4 months / PEMF group) $\neq \mu$ (Change in NPRS score at 4 months / sham group)

To compare the absolute change in pain from baseline to 4-months, the intra-patient change will be calculated and serve as the dependent variable in the analysis. The baseline pain score will be introduced in the model as a covariate. Clinical site will be added to the model to assess poolability of the data across sites. Interaction between clinical site and treatment will be evaluated using a type 1 error rate of 10%. A Mixed Models with Repeated Measures (MMRM) analysis comparing results across all time-points will also be performed, adjusted for the baseline value, week, treatment by week interaction and the effect of the patient.

The primary efficacy endpoint will be summarized and reported using the Level 3 table design. Results will be presented in Table 14.4.1.1 entitled Summary of the Pain Intensity by Randomized Treatment Assignment and Time (ITT Population)

Listing 16.2.8.1 entitled *Pain Intensity by Randomized Treatment Assignment and Time* will contain all of the recorded information; this listing will be sorted by subject number and relative study day.

A list of additional summary tables is presented in the table below.

Table	Description
14.4.1.1.1	Kaplan-Meier Estimates for the First Week where a Mean Reduction of 2 Points or a 30% Reduction from Baseline in the NPRS is Observed
14.4.1.1.2	Summary of the Pain Intensity Categorized by Success (>=30% reduction from baseline) by Randomized Treatment Assignment and Time
14.4.1.1.3	Summary of the Pain Intensity Categorized by Success (>=2 point reduction from baseline) by Randomized Treatment Assignment and Time
14.4.1.1.4	Summary of the Pain Intensity Categorized by Success (>=2 point reduction or 30% reduction from baseline) by Randomized Treatment Assignment and Time

Table	Description
14.4.1.2	Summary of the NeuroQoL Results by Question, Randomized Treatment Assignment and Time
14.4.1.2.1	Summary of the Efficacy Endpoints by Randomized Treatment Assignment and Time - NeuroQol (Weighted) Domain 1: Pain

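### SAP 7.2 rules out imputing missing values, while Protocol 7.1 plans pattern-mixture multiple imputation for the primary pain endpoint

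*SAP*

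**What the plan says.** **Protocol 7.1**, under its missing-data subheading, gives a full algorithm for the pain scores:

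- "If a patient reports at least 3 days with non-missing pain intensity scores within a particular week", the weekly mean is taken over the days reported. With fewer days, the week counts as missing.
- "Missing weekly mean pain intensity scores will be imputed using multiple missing data and pattern mixture methodology".
- Intermittent gaps are filled first by MCMC. Early discontinuations are then imputed according to the reason for leaving. For those leaving because of an adverse event or lack of response, "missing data will be assumed to follow a distribution similar to the baseline values observed in the" subject's own randomized arm. Other dropouts are imputed from same-arm subjects who are still in the study.
- "Results of the 120-day results, and the MMRM using the multiply imputed data, will be summarized using the SAS MIANALYZE procedure".
- "Sensitivity analyses will be conducted exploring different patterns for missing data".
- An observed-data MMRM and a change-to-last-available-week analysis are added alongside the imputation.

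**SAP 7.2** says: "Values for missing data will not be imputed, however a methodology is defined for missing dates". It offers a last-recorded-observation analysis as the comparison for the ITT population. SAP 11 gives a 4-month change model with baseline as covariate and an additional MMRM, neither with an imputation step. It then says: "The primary efficacy endpoint will be summarized and reported using the Level 3 table design". SAP 7 illustrates that layout with 18 subjects at baseline and 16 at Month 4, where "the difference (Month 4 minus Baseline) will contain 16 subjects". SAP 6 makes ITT the primary set.

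**The concern.** The two current documents give opposite instructions for missing data on the primary endpoint. Protocol 7 leaves the statistical detail to the SAP, and SAP 2 says its analyses are the basis for the study's conclusions. A programmer would therefore most likely follow the SAP and carry out no multiple imputation.

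Two things would then be lost. The first is the assumption that subjects who leave for an adverse event or lack of response have pain like that at baseline. The second is the set of pattern-based sensitivity analyses. There is also no statement of which remaining analysis decides the ITT result: the 4-month change model, which has no rule for an absent Month 4 value, or the last-observation comparison. Without that statement, the choice could be made after results are seen.

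**Working it through.** **Search of the SAP.** The visible SAP was read for any trace of the protocol's method.

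| Element of Protocol 7.1 | In the visible SAP? |
|---|---|
| 3-day rule for the weekly mean | No |
| MCMC for intermittent gaps | No |
| Imputation by discontinuation reason | No |
| MIANALYZE for the 120-day result and MMRM | No; the code in SAP 13.2 covers LIFETEST, PHREG, GLM, UNIVARIATE, FREQ/CMH and NPAR1WAY only |
| Sensitivity analyses over missing-data patterns | No |
| MMRM | Yes, SAP 11, with no mention of imputation |
| Last-value analysis | Yes, SAP 7.2, but as the last recorded observation, without saying that this is a weekly mean |

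SAP 7 mentions imputation algorithms only for dates. No declared departure from the protocol was found.

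**The plan's own figure.** Inputs from Protocol 7.4 and SAP 4.3: difference 1.07, SD 1.83, two-sided alpha 0.05, power 90%. The normal approximation gives n = 2(1.960 + 1.282)² × 1.83² / 1.07² = 61.5, so 62 per arm, as stated.

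**How many values are at issue.** Protocol 7.4 assumes 30% premature discontinuation: 0.30 × 170 = 51 without a Month 4 value, and 170 − 51 = 119 with one. SAP 4.3 describes the same inflation only as 1.3 × 124 ≈ 162. Read as retention, that implies (162 − 124)/162 = 23.5% loss, or about 40 of 170.

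**Illustration of what the rule can do.** Assumptions, not facts from the plan: the 60-day planning values stand in for the 4-month completer change, and dropouts for other reasons sit at their own arm's mean.

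- Sham change = 0.40 × 1.79 = 0.716. Completer difference = 1.79 − 0.716 = 1.074.
- Equal 30% dropout by arm, with s the share of dropouts due to adverse events or lack of response and imputed at no change: difference = 1.074 × (1 − 0.30s).
  - s = 0: 1.07
  - s = 0.5: 0.91
  - s = 1: 0.75
- Unequal dropout of this kind, with pA and pS the proportions of each arm affected: difference = (1 − pA) × 1.79 − (1 − pS) × 0.716.
  - 20% active, 10% sham: 1.432 − 0.644 = 0.79
  - 5% active, 15% sham: 1.701 − 0.609 = 1.09

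**Power.** Take the difference as 1.07 × (1 − q), where q is the share of each arm imputed at baseline, with SD held at 1.83 and 85 per arm (normal approximation):

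| q | Difference | Power |
|---|---|---|
| 0 | 1.07 | 0.97 |
| 0.10 | 0.96 | 0.93 |
| 0.20 | 0.86 | 0.86 |
| 0.30 | 0.75 | 0.76 |

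**The case against.** The conflict of wording cannot be explained away, but several points can fairly be made for the plan.

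- **Much of the protocol survives.** Protocol 7.1 itself plans an observed-data MMRM, a last-value analysis and tabulations for completers and for last recorded evaluations. What the SAP drops is the imputation layer, its sensitivity analyses and the 3-day rule. This stands as a description of the loss. In the protocol, though, the retained analyses accompany the imputation and do not replace it.
- **The Level 3 table is a descriptive layout.** It does not show that the hypothesis test is restricted to completers. This stands. The gap is that SAP 11 gives no rule for an absent Month 4 value.
- **Last observation can resemble the baseline-like rule.** A subject who leaves without having improved carries forward a score near baseline. This is partly right. The rules diverge for subjects who had improved before leaving, for example those who stop because of an adverse event.
- **The illustration does not size the conflict.** It compares completers with the protocol rule and does not compute the last-observation or MMRM results. This stands, and it is why the figures show only that the rule can matter.
- **The SAP may reflect a deliberate choice.** The front matter and the separate table index could not be seen. A deliberate choice would still need to be declared, and no visible section does so.
- **Early-termination assessments may fill the gap.** Protocol 5 asks for Month 4 assessments before withdrawal. The endpoint, however, is a 7-day average of diary scores at Day 120 (Protocol 3.12.1), which an earlier visit cannot supply.

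**Conclusion.** The concern holds and should be resolved before unblinding. It is a direct contradiction between current documents on the primary endpoint, and goes beyond missing detail. Between about 40 and 51 of 170 Month 4 values would be governed by whichever rule is followed, depending on how the sample-size inflation is read. The effect on the estimate is not determined, because the documents give neither the mix of discontinuation reasons nor their balance by arm. Under the stated assumptions, the protocol rule could leave the planned difference unchanged, reduce it to about 0.75, or raise it slightly if dropout for adverse events or lack of response is heavier on sham. The conclusion about the contradiction rests on the wording alone and does not depend on those figures.

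**What to change.** **Preferred.** Replace the no-imputation sentence in SAP 7.2 with the Protocol 7.1 algorithm for the 4-month pain comparison in the ITT set: the 3-day weekly mean, MCMC for intermittent gaps, pattern-mixture imputation by discontinuation reason, and MIANALYZE. Label the observed-data MMRM and the last-value analysis as supportive, and restore the pattern-based sensitivity analyses.

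Some details need settling when the text is carried over:

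- The protocol's first dropout rule lacks a conjunction between adverse event and lack of response. The following rule implies that either reason qualifies.
- Lack of response is not among the withdrawal circumstances in Protocol 5 or SAP 4.4. The termination reasons summarised under SAP 8 must identify it, or subjects must be classified while still blinded.
- State which 7-day window represents Day 120 (120 = 17 × 7 + 1, so whole weeks do not end there), the imputation-model variables and the number of imputations.

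**Alternative.** If the SAP approach is meant to govern, declare and justify the change, name the single deciding analysis, and keep the protocol's pattern-mixture imputation as a sensitivity analysis.

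**Cost.** SAP wording, programming for a method the protocol already describes, and possibly a blinded review of discontinuation reasons. The estimate may turn out less favourable.

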7.3. Multiple Comparison/Multiplicity

No adjustment for multiplicity will be applied to the type 1 error rate in the analysis of the endpoints from this study.

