All hypothesis tests comparing active and sham treatment will be two-sided and conducted at the 5% significance level based on Part A of the study. The primary population for assessing efficacy and safety will be the ITT population from Part A. A secondary analysis of the individual efficacy endpoints will be conducted using the Per-Protocol population from Part A. All summary tables will be presented by treatment group and over all patients in the analysis population being summarized. Continuous variables will be summarized using the following descriptive statistics: n, mean, SD, median, minimum, and maximum. Categorical variables will be summarized using counts and percentages. Percentages presented will be calculated using all patients in the analysis population being summarized (with randomized or received treatment as/if appropriate) as the denominator.

To compare the absolute change in pain from baseline to 4months, the intra-patient change will be calculated and serve as the dependent variable in the analysis. The baseline pain score will be introduced in the model as a covariate. Clinical site will be added to the model to assess poolability of the data across sites. Interaction between clinical site and treatment will be evaluated using a type 1 error rate of 10%.

Treatment-emergent adverse events will be summarized by study part, type, frequency, severity, and relationship to the study device. Adverse events will be provided in a listing.

SAS® Version 9.4 or later will be used to produce all statistical tables, listings and figures to be contained in the integrated statistical/clinical report.

Table of Contents

1.	INTRODUCTION AND BACKGROUND	.19
2.	STUDY OBJECTIVES	.24
3.	STUDY DESIGN	.25
3.1	Study Design	. 25
3.2.	EFFICACY ENDPOINTS	.26
3.3	SAFETY EVALUATION	.26
3.4	Eligibility Criteria	. 27
3.5	ENROLLMENT	. 30
3.6	RANDOMIZATION	. 30
3.7	DEVICE DESCRIPTION	. 30
3.7.1	Control Unit	. 30
3.7.2	Treatment Applicator	. 32
3.8	LOGISTICS AND DEVICE ACCOUNTABILITY	. 32
3.9	LABELING	. 33
3.10	Preparation and Administration	. 33
3.11	Blinding	. 33
3.12	Study Assessments	. 34
3.12.1	Primary Efficacy Assessment	. 34
3.12.2	Secondary Efficacy Assessments	. 34
3.12.3	Exploratory Efficacy Assessment	.37
3.12.4	Additional Study Assessments	. 38
3.12.5	Safety Assessments	. 40
4.	STUDY PROCEDURES	.40
4.1	VISIT 1 – SCREENING VISIT (DAY -15)	.40
4.2	14-Day Run-In Period	.42
4.3	Visit 2 – Enrollment Visit (Day 0)	.42
4.4	Day 7 Phone Call (Day 7 +2 Days)	.43

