3.12.2 Secondary Efficacy Assessments

NeuroQoL

The NeuroQoL is a validated 29 question assessment tool that measures the effects of diabetic peripheral neuropathy and its complications on an individual's quality of life. Subjects are asked about the effect their foot problems may have on their daily life and well-being in the past 4 weeks, with "foot problems" meaning lost or reduced feeling in the lower extremities, pain discomfort, and in some cases unsteadiness while walking or standing. The questionnaire will be completed by the

35

subject at the Enrollment Visit, Month 2, Month 4, Month 8, and Month 12 visit (Day 361).

Skin Perfusion Pressure

Vasamed Sensilase PAD-IQ measures the perfusion pressure (in mmHg) of microcirculation using a laser Doppler sensor. SPP uses the reactive hyperemia to assess capillary health in specific angiosomes. Two previous trials were conducted in patients with painful peripheral diabetic neuropathy showing an increase in circulation (pressure) from baseline.

The patient lies down in supine position and remains silent and still. The Laser Sensor Assembly (LSA) is inserted into the LSA Placement Guide and the optical sensor window is oriented toward the skin on the foot. A cuff is positioned so that the LSA is centered on the bladder both horizontally and vertically. The pressure of the cuff is then automatically increased to a pressure necessary to occlude blood flow and then released at a controlled rate and a measurement of the pressure in the angiosome is made. Skin Perfusion Pressure- SPP is the pressure required for restoring microcirculatory blood flow following release of carefully controlled occlusion. Two measurements are obtained per foot; one on the dorsal aspect of each foot in the distribution of the dorsalis pedis artery angiosome and on the plantar aspect of each foot in the distribution of the lateral plantar artery angiosome. SPP will be conducted at the Enrollment Visit to obtain a baseline value and at months 2, and 4. An increase in SPP would be considered clinically meaningful.

Sural Nerve Conduction Studies (NCS)

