Sural Nerve Conduction Studies (NCS) assess large myelinated axons. Using the NC-stat[®] DPNCheck[®], the subject will assume a comfortable position so that their right or left leg is visible (that the subject's outer ankle bone and Achilles tendon are visible). The patient preparation pad is then used to thoroughly clean the subject's outer lower leg and ankle bone area to remove any residue. The subject's lateral malleolar (ankle) bone is then identified to align the anode and cathode just behind with the cathode just adjacent to the middle of the ankle bone. The device is aligned on the calf pressing firmly down on the foam to ensure contact on either side of the calf. The sural nerve conduction velocity and amplitude will be recorded. The test will then be repeated on the opposite leg. NCS will be collected at the Enrollment Visit to obtain a baseline value and at Days 121 (month 4) and 361 (month 12). An increase in velocity and/or an increase in amplitude would suggest DPN improvement.

Quantitative Sensory Testing (QST)

Quantitative Sensory Testing (QST) for thermal sensation assesses small diameter unmyelinated and lightly myelinated axons. QST is a noninvasive technique providing an easy to use, validated measure of warm, cool, and heat pain thermal sensory thresholds.

The Thermal Stimulator is placed on the surface of the skin on the dorsal aspect of the foot. The Thermal Stimulator is held in place on the foot by a Velcro strap, which wraps around the subject's foot.

Contact thermal stimulation will be delivered using the Medoc Ltd. Q-Sense system. A Thermal Stimulator probe ("thermode") is placed on the surface of the skin on the dorsal aspect of the foot in the distribution of the superficial branch of the distal fibular (peroneal) nerve. The probe is held in place by a Velcro strap, which wraps around the subject's foot. Using a Patient Response Unit (PRU), the subject presses a button to identify their response to the delivered thermal stimulation. This is done by successful trials to assess cool sensation threshold (CS), warm sensation threshold (WS) and heat pain threshold (HP) modalities using the method of Limits. Within the cool and warm sensation modalities, the trial is repeated 4 times on each foot and 3 times on each foot for heat pain threshold modality. The cool thermal testing should be conducted prior to the warm and heat pain thermal testing.

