3.1.1. Efficacy Assessments and Endpoints

There will be 11 total endpoints from Part A of the protocol (Part B analysis is in a separate SAP); the interest will be in the change from baseline and the differences between active Provant therapy vs. sham.

Primary Endpoint: Absolute change from baseline in pain intensity as measured by the 11-point, numerical pain rating scale (NPRS) (0-10; where 0=no pain, to 10=worst possible pain) through 4 months.

Secondary Endpoint 1: Percentage of patients who have either a 2 point or 30% reduction in NPRS at 4 Months.

Secondary Endpoint 2: Time to 30% or 2-point reduction in NPRS, whichever comes first at 4 Months.

Secondary Endpoint 3: Change in neuropathy related quality of life (NeuroQoL) between baseline and end of treatment at 4 Months.

Secondary Endpoint 4: Changes in Skin Perfusion Pressure (SPP) from baseline to end of treatment at 4 Months.

Secondary Endpoint 5: Changes in Nerve Conduction Studies (NCS) of Velocity and/or Amplitude between baseline and end of treatment at 4 Months.

Secondary Endpoint 6: Changes in Quantitative Sensory Testing (QST) between baseline and end of treatment at 4 Months.

Secondary Endpoint 7: Change in Patient Global Impression (PGI) at 4 Months.

Exploratory Endpoint 1: Change in Work Productivity and Impairment Questionnaire (WPAIQ) **Exploratory Endpoint 2:** Changes in intraepidermal nerve fiber density (IENFD) at the distal thigh.

Exploratory Endpoint 3: Changes in IENFD at the distal leg.

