14.4.1.2.1a	Summary of the Efficacy Endpoints by Randomized Treatment Assignment and Time - NeuroQol (Unweighted) Domain 1: Pain
14.4.1.2.2	Summary of the Efficacy Endpoints by Randomized Treatment Assignment and Time - NeuroQol (Weighted) Domain 2: Lost/reduced feeling
14.4.1.2.2a	Summary of the Efficacy Endpoints by Randomized Treatment Assignment and Time - NeuroQol (Unweighted) Domain 2: Lost/reduced feeling
14.4.1.2.3	Summary of the Efficacy Endpoints by Randomized Treatment Assignment and Time - NeuroQol (Weighted) Domain 3: Diffuse sensory-motor symptoms
14.4.1.2.3a	Summary of the Efficacy Endpoints by Randomized Treatment Assignment and Time - NeuroQol (Unweighted) Domain 3: Diffuse sensory-motor symptoms
14.4.1.2.4	Summary of the Efficacy Endpoints by Randomized Treatment Assignment and Time - NeuroQol (Weighted) Domain 4: Restrictions in activities of daily living
14.4.1.2.4a	Summary of the Efficacy Endpoints by Randomized Treatment Assignment and Time - NeuroQol (Unweighted) Domain 4: Restrictions in activities of daily living
14.4.1.2.5	Summary of the Efficacy Endpoints by Randomized Treatment Assignment and Time - NeuroQol (Weighted) Domain 5: Disruptions in social relationships
14.4.1.2.5a	Summary of the Efficacy Endpoints by Randomized Treatment Assignment and Time - NeuroQol (Unweighted) Domain 5: Disruptions in social relationships
14.4.1.2.6	Summary of the Efficacy Endpoints by Randomized Treatment Assignment and Time - NeuroQol (Weighted) Domain 6: Emotional distress
14.4.1.2.6a	Summary of the Efficacy Endpoints by Randomized Treatment Assignment and Time - NeuroQol (Unweighted) Domain 6: Emotional distress
14.4.1.3	Summary of the Skin Perfusion Pressure Results by Randomized Treatment Assignment and Time
14.4.1.4	Summary of the Nerve Conduction Results by Randomized Treatment Assignment and Time
14.4.1.5	Summary of the QST Results by Randomized Treatment Assignment and Time
14.4.1.6	Summary of the Work Productivity and Activity Impairment Questionnaire (WPAIQ) by Visit and Randomized Treatment Assignment
14.4.1.7	Summary of the Patient Global Impression (PGI) by Visit and Randomized Treatment Assignment
14.4.1.8	Summary of Treatment Satisfaction by Visit and Randomized Treatment Assignment
14.4.1.10	Summary of the Toronto Clinical Neurpathy Scoring System by Randomized Treatment Assignment and Time

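### The protocol promises hierarchical testing of the secondary endpoints, but the SAP has no testing sequence, gate or adjustment, and secondaries 3 to 7 have no named deciding variable

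*SAP*

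**What the plan says.** Protocol 7.1 closes with the multiplicity rule: "A hierarchical approach will be undertaken for the pre-specified secondary outcomes. Testing will occur in the listed sequence following testing of the primary endpoint". The synopsis, under Statistical Considerations, sets one level for everything: "All hypothesis tests comparing active and sham treatment will be two-sided and conducted at the 5% significance level".

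Protocol 7 leaves the detailed analysis to the SAP. The only multiplicity text there is SAP 7.3: "No adjustment for multiplicity will be applied to the type 1 error rate in the analysis of the endpoints from this study". The conventions in SAP 7 add: "P-values <0.05 will be considered to be statistically significant". SAP 3.1.1 numbers the secondaries 1 to 7 in the protocol's order but does not call this a test order. SAP 11 states a formal hypothesis for the primary endpoint only.

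Secondaries 1 (responder at 2 points or 30%) and 2 (time to that response) are each a single variable. The other five are not:

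- **3, NeuroQoL:** SAP 11 lists six domains, each weighted and unweighted, ending with "NeuroQol (Weighted) Domain 6: Emotional distress". There is no total score and no lead domain.
- **4, skin perfusion pressure:** "Two measurements are obtained per foot; one on the dorsal aspect of each foot" and the other on the plantar aspect (Protocol 3.12.2). No summary is defined.
- **5, nerve conduction:** "Changes in Nerve Conduction Studies (NCS) of Velocity and/or Amplitude between baseline and end of treatment at 4 Months" (SAP 3.1.1), measured on both legs.
- **6, sensory testing:** repeated trials on each foot to "assess cool sensation threshold (CS), warm sensation threshold (WS) and heat pain threshold (HP) modalities" (Protocol 3.12.2).
- **7, PGI:** three questions, first asked at Month 1 (Protocol 3.12.2 and Appendix A). Questions 1 and 2 therefore have no baseline, and only question 3 expresses a change.

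**The concern.** A fixed sequence controls error through two features: testing stops at the first failure, and each step has one hypothesis fixed in advance. The protocol gives an order but states neither feature. The SAP drops the order as a testing rule and lets any p-value below 0.05 count.

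Two things follow. A secondary can be declared significant after the primary, or an earlier secondary, has failed. And at steps 3 to 7 the component that decides the step can be chosen after the data are seen. SAP 2 says that the planned analyses may go into regulatory submissions and manuscripts, so these results could be presented as findings. What is at stake is the secondary claims. The primary comparison, its alpha and the sample size do not depend on this.

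**Working it through.** **Inputs.** Two-sided 0.05 per test (Protocol synopsis; SAP 7). Seven secondaries (SAP 3.1.1). The documents give no correlations between endpoints, so equal correlation ρ between the test statistics is assumed, at 0, 0.5 and 0.9. They also state no family-wise error for the secondaries, so there is no figure of the plan's own to reproduce on this point.

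**Component count.** Responder 1 + time to response 1 + NeuroQoL domains 6 + skin perfusion 1 + nerve conduction 2 + sensory thresholds 3 + PGI questions 3 = 17. This averages feet, legs and perfusion sites, and counts the weighted and unweighted NeuroQoL scores once.

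**Formula.** With c = 1.96 and k null tests,

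P(at least one p < 0.05) = 1 − ∫ φ(u) [Φ((c − √ρ·u)/√(1−ρ)) − Φ((−c − √ρ·u)/√(1−ρ))]^k du.

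At ρ = 0 this is 1 − 0.95^k: for k = 7, 1 − 0.698 = 0.302; for k = 17, 1 − 0.418 = 0.582.

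The primary (if null) fails and at least one null secondary is below 0.05 with probability P(any of k + 1) − 0.05. At ρ = 0 and k = 7 this is 0.337 − 0.05 = 0.287.

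| Event, all tests null | ρ = 0 | ρ = 0.5 | ρ = 0.9 |
|---|---|---|---|
| Any of 7 secondaries below 0.05 | 0.302 | 0.230 | 0.114 |
| Any of 17 components below 0.05 | 0.582 | 0.386 | 0.149 |
| Primary fails, any of 7 below 0.05 | 0.287 | 0.200 | 0.069 |
| Primary fails, any of 17 below 0.05 | 0.553 | 0.348 | 0.101 |
| Step 3 passes on any of 6 NeuroQoL domains | 0.265 | 0.207 | 0.108 |
| Step 5 passes on velocity or amplitude | 0.098 | 0.091 | 0.070 |

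**Comparator.** In a fixed sequence with one test per step and all secondaries null after a passed primary, a false claim requires step 1 to reject, which has probability 0.05. Simulation of 400,000 trials gave 0.050 at each of the three correlations.

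The last two rows of the table show that restoring the order alone is not enough. If a step can pass on whichever component is significant, its own false-pass rate exceeds 0.05 even at ρ = 0.9.

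**The case against.** The strongest reply is that the two documents can be read together. A fixed sequence tests each step at an unadjusted 0.05, so a statement of no adjustment does not exclude one, and the SAP keeps the protocol's order. A statistician would normally take a hierarchical approach to imply stopping at a failure. The sentence on p-values below 0.05 sits in a bullet about number formatting. All of that is fair, and the SAP's fault is partly omission. But SAP 7.3 is the operative text on multiplicity. It mentions no hierarchy or gate, and the protocol says only that the secondaries follow the testing of the primary, not its success.

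Three further points concern size.

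- **Direction.** The figures count significant results in either direction. Counting only those favouring active treatment, at ρ = 0, 0.5 and 0.9, gives 0.16, 0.11 and 0.06 for 7 tests and 0.35, 0.19 and 0.07 for 17. This stands, but the fixed-sequence comparator also halves, to 0.025, so the relative inflation is much the same.
- **Correlation and count.** Independence is not credible across the whole set, since secondaries 1 and 2 come from one pain diary and the NeuroQoL domains from one questionnaire. The count of 17 is a construction: the SAP's tables for secondaries 3 to 7 are titled as summaries, and their layout shows no p-values. The lower end of the range is therefore relevant too.
- **PGI.** Question 3 is a usable variable that needs no baseline. That is so, but neither document names it as the deciding one.

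None of these supplies a stopping rule or a deciding variable for steps 3 to 7.

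**Conclusion.** The concern holds. The SAP as written does not carry out the protocol's hierarchy, and the hierarchy cannot be carried out beyond step 2 with the definitions given. Depending on an assumed common correlation between 0 and 0.9, the chance of at least one false secondary finding is 0.11 to 0.30 over seven tests and 0.15 to 0.58 over 17 components, against 0.05 under a properly specified sequence. These figures assume that all secondaries are null and that the component tests are actually run. The conflict between the documents does not depend on either assumption. It must be resolved before Part A is unblinded, because a stopping rule or deciding variable chosen afterwards cannot restore the error control.

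**What to change.** Before Part A is unblinded, choose one of two resolutions and write it into both documents.

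1. **Keep the hierarchy.** Replace SAP 7.3 with the sequence: primary at two-sided 0.05, then secondaries 1 to 7 in listed order, with confirmatory testing stopping at the first p-value of 0.05 or more. For each of steps 3 to 7 name one variable, one summary score or an all-components rule, and say how feet, legs and sites are combined. For PGI, use question 3 or state that questions 1 and 2 are compared as Month 4 values. Report the other components descriptively, and limit the significance sentence in SAP 7 to the sequence. Add the same stopping rule and definitions to Protocol 7.1 and the endpoint list.
2. **Drop the hierarchy.** Amend Protocol 7.1 to remove it and label all secondaries descriptive in both documents.

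Either route is a wording change, with no new data or patients and no change to the primary test or the planned 170 subjects. The price is that some nominal p-values become descriptive.
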